In a separate study, we found that fluoroquinolones are frequently prescribed for extended surgical prophylaxis in patients undergoing urologic procedures.¹⁶ The frequent use of fluoroquinolones is concerning given the strong association between fluoroquinolone use and several adverse events, including CDI.¹⁷

In December 2018, our study team surveyed 110 hospitals within the research network of the Society for Healthcare Epidemiology of America. Forty hospitals (36.4%) responded. Among the 38 hospitals that performed urologic procedures, 18 (47.4%) had never audited whether urologists at their facility adhered to the AUA guidelines for post-procedural antimicrobial use. In the hospitals that did audit, 30% reported that antimicrobials were always prescribed for more than 24 hours. Another 30% reported prolonged post-procedural courses were prescribed in some patients.

These findings suggest that there is an unrecognized opportunity to evaluate and potentially improve antimicrobial-prescribing in patients undergoing urologic procedures. The following study will leverage audit-and-feedback plus additional implementation strategies with the goal of reducing unnecessary post-procedural antimicrobial use after 3 common urologic procedures. The findings from this pilot trial could inform a larger intervention across the VHA to reduce the use of excessive post-procedural antimicrobial prophylaxis in urologic patients.

METHODS

Trial design:

We will use a before/after quasi-experimental design, which will be analyzed with an interrupted time-series analysis.

Participants:

Eligibility criteria: There will be 3 intervention VHA hospitals. To be eligible, a VHA hospital must perform the following 3 urologic procedures: transurethral resection of the prostate (TURP), transurethral resection of a bladder tumor (TUBRT), and ureteroscopy (URS). Eligible VAMCs needed to perform these three index procedures, perform at least 75 qualifying procedures per year, and utilize excess post-procedural antimicrobial in the highest tertile for all sites.

Method of recruitment: The Chief of Urology at an eligible intervention sites will be contacted by e-mail. A follow-up Microsoft Teams or Zoom call will be scheduled to explain the project, if the Chief of Urology is interested in potentially participating.

Interventions:

- Content: Feedback on the percentage of patients who underwent a qualifying procedure and received an antimicrobial on post-procedural day 1

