the 2-year baseline period or during the 1-year intervention period. These three procedures were selected because they are all common procedures performed endoscopically with no skin incision required. In addition, for all 3 procedures, the AUA guidelines give a clear recommendation for giving a single dose of antimicrobial prophylaxis.¹⁵

Secondary outcomes

Excess post-procedural antimicrobial duration is defined as the duration of continuous excessive post-procedural antimicrobial use, as quantified as days of therapy per National Healthcare Safety Network methodology.¹⁹

Safety outcomes

- Late antimicrobial prescription is defined as the prescription of a designated antimicrobial that does not qualify as a post-procedural antimicrobial (see above) by any provider within 7-30 days of the date of the patient's urologic procedure. All late antimicrobial prescriptions must be agents potentially used for a urinary tract-related indication, as outlined in our prior work.⁵
- Return visits: seeking care in an Emergency Department, Urgent Care Clinic or hospital readmission to an acute-care bed at a VHA facility for any indication within 30 days of the patient's index urologic procedure.

Assignment Method: Intervention sites will be selected from the top tertile of all sites, as ranked on the frequency of excess post-procedural antimicrobial-prescribing. Eligible new sites will be invited until 3 unique sites agree to participate.

Sample Size: This was a pilot trial, so no sample size calculation was performed.

Blinding: None

Unit of Analysis: Each medical center (3 intervention)

Statistical Methods:

Patient demographics, comorbidities, and types of procedures are presented by count and percentages. Observations occurring within the implementation phase (July 2022) were omitted from all analyses. Observations from each of the three sites were stratified into three data sets to accommodate separate analyses on each site.

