To model the primary outcome, we used a logistic regression model and a set of three explanatory variables: time, a binary indicator for an observation occurring within the intervention phase, and an interaction term between these two main effects (time and intervention). Time was measured in days divided by 365, giving an annualized figure for the time coefficient estimate and interaction coefficient. In the tables of results of these logistic regression models, the coefficient estimates are exponentiated to display estimated multiplicative effect on the odds; 95% confidence intervals are also provided on the odds scale. The median duration of post-procedural antimicrobial prescriptions at each site were compared using the Wilcoxon rank-sum test.

To model the secondary outcomes, we used a similar approach to what is described above with the addition of a fourth explanatory variable (a binary indicator for the primary outcome) to the

logistic regression model. This last variables was included to assess the risk of these secondary outcomes in patients who were not exposed to post-procedural antimicrobials compared to those who were exposed.

References:

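### Excess duration has only a per-site rank-sum test with no time term as its workable analysis, so a prior trend in course length cannot be separated from a change after feedback began

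*Combined protocol and SAP*

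**What the plan says.** All references are to the combined protocol and SAP, Version 1.2, dated 8 March 2024.

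- **Trial design** describes a before/after quasi-experiment "which will be analyzed with an interrupted time-series analysis".
- **Statistical Methods, primary outcome**: a logistic model at each site with "time, a binary indicator for an observation occurring within the intervention phase, and an interaction term between these two main effects".
- **Outcomes, Secondary outcomes**: one item only. "Excess post-procedural antimicrobial duration is defined as the duration of continuous excessive post-procedural antimicrobial use, as quantified as days of therapy".
- **Statistical Methods, duration**: "The median duration of post-procedural antimicrobial prescriptions at each site were compared using the Wilcoxon rank-sum test". The sentence does not name the groups compared or say that only recipients enter.
- **Statistical Methods, next paragraph**: "To model the secondary outcomes, we used a similar approach to what is described above", with the primary-outcome indicator as a fourth covariate. Its stated purpose is to compare risk in patients exposed and not exposed to post-procedural antimicrobials. Late antimicrobial prescription and return visits, which suit that purpose, are listed under Safety outcomes.
- **Calendar**: "the 2-year baseline period or during the 1-year intervention period"; "Observations occurring within the implementation phase (July 2022) were omitted from all analyses".
- **Participants**: a site must "perform at least 75 qualifying procedures per year".

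**The concern.** A two-sample rank-sum test attributes the whole difference between phases to the phase. If courses were already getting shorter, the test counts that fall as a change after feedback; if they were getting longer, it hides a real shortening. The declared design exists to deal with this, and the plan applies it to the primary outcome but not to duration.

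What is at stake is limited: one secondary outcome in a three-site pilot. But the Background says the pilot could inform a larger VHA intervention, and duration is its only measure of course length.

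**Working it through.** **1. Is there another analysis of duration with a time term?** Read literally, the logistic model for secondary outcomes covers duration, because duration is the only item under that heading. As written it cannot serve. Duration is a count of days and no cut-point is given. The fourth covariate is the primary outcome, which decides whether a patient has any excess duration at all. The stated purpose fits the two binary safety outcomes. So the labels in Outcomes and Statistical Methods do not agree, and no workable time-adjusted analysis of duration is specified.

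**2. How much drift would the comparison absorb?** The plan gives no figure to reproduce. Taking the baseline to end where the omitted month begins:

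Gap between phase midpoints = 2/2 + 1/12 + 1/2 = 1.583 years (19 months).

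Apparent shortening from a steady fall of d a year, with no intervention effect = 1 − (1 − d)^1.583:

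- d = 2%: 1 − 0.98^1.583 = 3.1%
- d = 5%: 1 − 0.95^1.583 = 7.8%
- d = 10%: 1 − 0.90^1.583 = 15.4%

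**3. How often would one site's rank-sum test be falsely positive?** This was simulated with 2,000 trials per setting and no intervention effect.

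- From the documents: the calendar; 75 procedures a year (a minimum); excess use after 37.2% of procedures and a median of 3.0 excess days (national cohort, Background); and 55.0%, which is the upper quartile across hospitals for bladder tumour resection only.
- Assumed: a two-sided 5% level; drift; 150 and 300 procedures a year; 60% use; duration equal to 1 plus a negative binomial count (k = 0.7, 1 or 3), with mean 3 or with median 3.0 (means 3.45 to 4.72); use constant over time.

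At 75 a year the recipients per site are about 56 v 28 at 37.2% use (75 × 2 × 0.372; 75 × 0.372) and 90 v 45 at 60%.

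| Drift a year | 75/year | 150/year | 300/year |
|---|---|---|---|
| none | 4-6% | 4-6% | 4-6% |
| 2% | 4-6% | 4-7% | 5-8% |
| 5% | 6-11% | 6-17% | 8-29% |
| 10% | 8-30% | 13-52% | 21-80% |

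The level-change test from a quasi-Poisson model with time, phase and time × phase stayed at 3-6% throughout.

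**4. The other direction.** With 60% use and a true 25% shortening, an upward drift of 5% a year cuts rank-sum power from 25-68% to 15-44% at 75 a year, and from 76-100% to 48-95% at 300.

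**5. What the segmented model cannot do.** Step 3 assumes that who receives a course is unrelated to its length. A selective fall from 60% use was also simulated, with no patient's duration changed. Keeping 50% of short and 80% of long courses, the recipients-only level-change test rejected in about 8% of trials at 75 a year and 12-16% at 300 (rank-sum 14-18% and 47-49%). Keeping 35% and 90%, it rejected in 10-14% and 28-36% (rank-sum 44-46% and 95-96%). The model does better than the rank-sum test here but is not immune.

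**The case against.** The strongest reply is that the harm is a possible over-reading, not an error in a stated conclusion. The plan models the primary outcome but only compares durations, and it draws no causal claim from that comparison. The documents report no trend in course length, and at the only volume they give, modest drift does little. Labelling the test as unadjusted would remove most of the problem. The Statistical Methods are in the past tense and the 12 months after July 2022 had ended before March 2024, so a new model would probably be post hoc, and it has little power at small sites.

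Most of this stands, and it sets the priority. What does not follow is that nothing should be added: duration is a named secondary outcome in a declared interrupted time series, and much of the rank-sum test's power advantage rests on an absence of trend that the plan never checks.

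A reader might also infer that the segmented model would settle whether feedback shortened courses. It would not. Feedback is aimed at who receives an antimicrobial on day one, so recipients before and after may be different groups, and the model removes only a log-linear trend.

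**Conclusion.** The gap is real and minor. For excess duration the plan has no workable analysis that separates a pre-existing trend from a change after feedback began, and its outcome labels need reconciling.

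At 75 procedures a year the inflation is small below an assumed drift of about 5% a year (about 6-11% false positives at 5%). It becomes large only with steeper drift or higher volume, neither of which the documents give. Top-tertile sites may well exceed 37.2% use, and volumes may exceed 75, but that is not stated.

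A reader might infer that the duration result is biased, or that the trial's main finding is in doubt. The documents support neither: they show no drift, and the primary model includes time. That the rank-sum test compares baseline with intervention among recipients is itself an inference from the design and the outcome definition, though a likely one; under any other grouping it would still lack a time term.

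**What to change.** 1. Keep the rank-sum test with median (IQR) by phase. State that it compares baseline with intervention among recipients, and label it an unadjusted before/after comparison. Plot duration over time by site.
2. Beside it, fit by site a log-link quasi-Poisson (or negative binomial) model of days of therapy among recipients, with time (zero at intervention start), phase and time × phase. Report level-change and slope-change ratios with 95% CI.
3. Interpret that model only as a change in duration among recipients beyond a log-linear trend, not as proof that the intervention shortened courses.
4. Report days of therapy per qualifying procedure, over all procedures, as a named supporting analysis with a different estimand.
5. State that the logistic model for secondary outcomes covers late antimicrobial prescription and return visits.
6. If intervals are too wide to be informative, say so. If duration results are already known, label the new analyses post hoc.

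**Cost.** Some wording, one plot and two models on data already extracted. The main downside is precision. With 60% use, no drift and a true 25% shortening, the segmented model's joint test of phase and time × phase has about 9-23% power at 75 a year, against 25-68% for the rank-sum test; at 300 a year it is 30-73% against 76-100%. If use stays at 60%, the upper limit of the level-change 95% CI is 2.5-4.4 times the lower at 75 a year and 1.6-2.1 times at 300. If use falls from 60% to 38%, these become 2.9-5.8 and 1.7-2.4, and the all-procedures model is wider still (4.9-8.1 and 2.2-2.9).

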The Surgical Care Improvement Project (SCIP) also used audit-and-feedback to improve antimicrobial-prescribing among surgical inpatients. SCIP was a nationwide initiative to reduce surgical complications through accountability and public disclosure. Ambulatory surgeries and urologic procedures were not included in SCIP. Compliance with SCIP standard 3, the discontinuation of antimicrobials within 24 hours of the operation, increased from <60% at baseline to 94% in 2012.¹³ These improvements were achieved even before CMS tied SCIP measures to hospital reimbursements in fiscal year 2013.

Although audit-and-feedback has been effective in improving antimicrobial-prescribing among certain types of surgical specialties, its benefit among urologic providers is unclear. In 2015, urologists accounted for the 8th highest number of outpatient antimicrobial prescriptions among all specialties.¹⁴ Given such a high frequency of antimicrobial-prescribing, there may be opportunities for enhanced antimicrobial stewardship among urologists.

The Best Practice Policy Statement on Urologic Surgery Antimicrobial Prophylaxis, published by the American Urological Association (AUA), recommends single-dose antimicrobial prophylaxis without post-procedural continuation is recommended for most urologic procedures.¹⁵

However, the unnecessary use of post-procedural antimicrobials is common after urologic procedures, according to administrative data our group analyzed from the VHA. In a national

cohort of nearly 30,000 patients, extended post-procedural antimicrobials (defined as >24 hours) were prescribed after 37.2% of urologic procedures for a median duration of 3.0 excess days.⁵ Based on a manual chart validation, 177 of 211 (83.9%) patients who received excessive post-procedural antimicrobials (i.e. more than 24 hours after the procedure) did not have a clear indication for antimicrobial therapy. At the hospital-level, the use of excessive post-procedural antimicrobials varied widely. For example, after transurethral resection of bladder tumors, the median frequency of excessive post-procedural antimicrobial-prescribing at the hospital-level was 27.9% with an interquartile range of 14.7-55.0%. Overall, we estimate that there are 30,000 days of unnecessary antimicrobial therapy per year in VHA patients undergoing these three urologic procedures.

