- Delivery method: At baseline, feedback will be given via a video-conferencing call in which we show the team their feedback report and explain what it means. All subsequent feedback will be delivered through e-mail.
- Unit of delivery: The feedback will be given to all practicing urologists at a site.
- Deliverer: The baseline video-conferencing call will be attended by the study team (Drs. [name], [name] and [name]). The electronic feedback will be sent from the PI's e-mail account.
- Setting: The intervention will be delivered via video-conferencing (baseline) or via e-mail (months 1, 3, 5, 7, 9, and 11).
- Exposure quantity and duration: Feedback will be given at baseline and every 2 months
- Time span: 12 months
- Activities to increase compliance or adherence: During the introductory call, the study team will review the AUA's guidelines on antimicrobial prophylaxis and the potential harms of extending antimicrobial prophylaxis beyond a single dose.^{15,18} The Chief of Urology at each site will be encouraged to be a local champion for more judicious use of post-procedural antibiotics.

Objectives:

- Study objectives: Evaluate whether a pilot audit-and-feedback intervention across 3 hospitals can safely reduce the unnecessary use of post-procedural antimicrobials in patients undergoing urologic procedures.
- Hypotheses: An bundled intervention across 3 hospitals will facilitate safe reductions in post-procedural antimicrobial-prescribing.

Outcomes:

Clinical outcomes are listed below. Data for all clinical outcomes will be extracted from the Corporate Data Warehouse (CDW) using the VA Informatics and Computing Infrastructure (VINCI).

Primary outcome

Excess post-procedural antimicrobial use is defined as a prescription for a designated antimicrobial agent on post-procedural day one. Designated antimicrobials will be antimicrobial agents potentially used for a urinary tract-related indication, as outlined in our prior work.⁵ This definition will be used to minimize the chance of including patients receiving antimicrobials for non-urologic or non-prophylactic indications.

Patients will be eligible for this outcome if they underwent a medical procedure coded with a Current Procedural Terminology (CPT) code or an International Classification of Diseases, 10th version, Procedure Coding System (ICD-10-PCS) code for TURPs, TURBTs, and URSs during

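### The duration comparison appears to use only patients who received a course, a group the intervention is meant to change, so it cannot separate course length from who is treated

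*Combined protocol and SAP*

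**What the plan says.** Under Outcomes, the single item listed as a secondary outcome reads: "Excess post-procedural antimicrobial duration is defined as the duration of continuous excessive post-procedural antimicrobial use, as quantified as days of therapy". The Statistical Methods section gives its analysis in one sentence: "The median duration of post-procedural antimicrobial prescriptions at each site were compared using the Wilcoxon rank-sum test". That sentence does not name the two groups. Since the data are split by site, baseline against intervention phase is the reading that fits.

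Three other places matter:

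- Primary outcome: "Excess post-procedural antimicrobial use is defined as a prescription for a designated antimicrobial agent on post-procedural day one". Eligibility is written for this outcome and covers all qualifying TURP, TURBT and ureteroscopy procedures.
- Interventions, content of the feedback: "Feedback on the percentage of patients who underwent a qualifying procedure and received an antimicrobial on post-procedural day 1".
- Objectives: the study asks whether the intervention "can safely reduce the unnecessary use of post-procedural antimicrobials in patients undergoing urologic procedures".

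No rule gives a duration to a procedure that was not followed by a prescription. No measure of total exposure, such as days of therapy per 100 procedures, is planned. The logistic model described for the secondary outcomes carries an indicator for the primary outcome and speaks of risk, so it fits the two binary safety outcomes and not duration.

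**The concern.** If only recipients enter the comparison, entry depends on an event that happens after the intervention starts and that the intervention is designed to prevent. Baseline recipients are everyone the site then chose to treat. Intervention-phase recipients are those still treated after feedback. Their durations can differ even if no prescriber changed the length of any course, and can agree even though many courses were stopped.

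Adding a time term would not cure this, so it is a separate matter from the absence of time adjustment in the rank-sum test. At stake is the meaning of the only secondary efficacy outcome in a pilot that is intended to inform a wider VHA programme.

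**Working it through.** **Is the set recipients only?** Duration is defined as the duration of excess use, and the analysis concerns the duration of prescriptions. Both presuppose a prescription. The Background reports an earlier national cohort in the same style: antimicrobials "were prescribed after 37.2% of urologic procedures for a median duration of 3.0 excess days". With 37.2% receiving a course, 62.8% have 0 excess days, so a median over all procedures would be 0. The 3.0 days must describe recipients. This supports the reading but does not prove it for the present trial.

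The plan gives no power or sample-size figure to reproduce. The rest is illustration.

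**Small worked example (all numbers assumed; 100 procedures per phase).** Baseline has 55 recipients: 33 with 3 days and 22 with 7 days. Excess days = 33×3 + 22×7 = 99 + 154 = 253; mean 253/55 = 4.6; median 3. In the intervention phase 20 courses stop and no remaining course changes length. The rank-sum test compares recipients only.

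| Stopped: 3-day / 7-day | Recipients' median | Excess days per 100 | p (recipients only) |
|---|---|---|---|
| 20 / 0 | 3 to 7 | 253 to 193 | 0.036, towards longer |
| 18 / 2 | 3 to 7 | 253 to 185 | 0.12 |
| 16 / 4 | 3 to 7 | 253 to 177 | 0.29 |
| 14 / 6 | 3 to 3 | 253 to 169 | 0.60 |
| 12 / 8 (proportional) | 3 to 3 | 253 to 161 | 1.0 |

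First row: 13×3 + 22×7 = 39 + 154 = 193, a fall of 60/253 = 24%. The mean rises to 193/35 = 5.5. The reversal is significant only in this extreme row, and the jump from 3 to 7 arises because only two durations are possible.

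**Simulation with a fuller distribution (4,000 runs per scenario, two-sided 0.05).**

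- From the plan: at least 75 qualifying procedures per year, a 2-year baseline and a 1-year intervention, giving 150 and 75 procedures per site at the minimum volume.
- Assumed: durations of 1, 2, 3, 4, 5, 6, 7 and 10 days with probabilities 0.18, 0.20, 0.25, 0.10, 0.12, 0.03, 0.10 and 0.02 (median 3, mean 3.41).
- Assumed baseline receipt: 55%, the upper quartile in the Background's hospital-level figure after bladder tumour resection (the median "was 27.9% with an interquartile range of 14.7-55.0"%). Sites are to come from the top tertile. 37.2% and 75% were also tried.

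Days per 100 procedures = 100 × receipt × mean days among recipients. Baseline: 100 × 0.55 × 3.41 = 187.6. For scenario (b), the fraction of courses kept is 0.63×0.3 + 0.37 = 0.559, so receipt is 0.55×0.559 = 30.7%. Days kept per baseline course are 1.33×0.3 + 2.08 = 2.479, so days per 100 are 55×2.479 = 136.3.

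| Courses stopped | Recipients' median | Recipients' mean | Days per 100 | Significant, recipients only |
|---|---|---|---|---|
| (a) 80% of 1-2 day, 30% of 3 day | 3 to 4 | 3.41 to 4.38 | 187.6 to 149.7 | longer, 66% of runs |
| (b) 70% of 1-3 day | 3 to 4 | 3.41 to 4.43 | 187.6 to 136.3 | longer, 58% |
| (c) 35%, any length | 3 to 3 | 3.41 to 3.41 | 187.6 to 121.9 | either way, about 5% |
| (d) 80% of 5 days or more | 3 to 3 | 3.41 to 2.64 | 187.6 to 113.6 | shorter, 40% |

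For (b), the wrong-way rate is 42% at 37.2% receipt and 72% at 75%. A rank-sum test over all procedures, with zeros, was significant for shorter in 74% of runs for (b) at 55% receipt, and for longer in none.

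**The case against.** Four points on the other side deserve weight.

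- **The analysis set is inferred.** This stands. No section states it, and the definition leans on a cited surveillance methodology that is not reproduced. Recipients only is the natural reading, not a certainty. The 37.2% and 3.0-day figures describe an earlier cohort and did not plan this trial. If all procedures were meant, the text still needs changing, because the median would be 0 at any site with receipt below 50%.
- **Course length among recipients is a fair descriptive question, and receipt is modelled separately.** This also stands. The primary analysis shows any fall in receipt beside the duration result, and the plan gives the rank-sum comparison no explicit causal reading. In scenario (c), no change in course length is a correct description of recipients. What remains is that a formal test between phases invites a reading as an intervention effect, and neither analysis gives total exposure, although the Background sizes the problem in days of therapy.
- **The reversal needs selective stopping.** This stands. A reader might infer that duration will look longer because the courses left are those prescribers were least willing to stop. The documents do not say which courses would stop, and reluctance to stop a course does not make it a long one. With 2 of the 20 stopped courses long, p is already 0.12.
- **A rank-sum test with zeros largely re-tests receipt.** This is true, and is why that test is not the analysis recommended below.

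**Conclusion.** The concern holds in a conditional form. As worded, the duration comparison appears to condition on receipt, which the intervention targets, so it cannot isolate an effect on course length. It may show apparent lengthening while exposure falls (58% to 66% of runs in the short-course scenarios at 55% receipt), no change despite a 35% fall in exposure, or apparent shortening when no remaining course was shortened (40%). Which of these would occur is unknown. The percentages rest on the assumed durations, stopping patterns and receipt rates, and on the minimum site volume.

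A reader might go further and conclude that the trial's efficacy result is compromised. The documents do not support that: the primary outcome is analysed over all eligible procedures and is untouched. The defect is confined to one secondary outcome in a three-site pilot, and it should be corrected.

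**What to change.** 1. State the analysis set for duration and the two groups compared.
2. Analyse excess days of therapy over every procedure eligible for the primary outcome, scoring 0 where there was no day-one use. Report days per 100 procedures by site and phase with a confidence interval.
3. Use a model for counts with many zeros, such as a negative binomial or two-part model, with the same time, intervention and interaction terms as the primary analysis. With a two-part model, report the combined mean days, since the second part alone is again conditional on receipt.
4. Do not use a median over all procedures, which is 0 whenever receipt is below 50%.
5. Keep the recipients' median as a descriptive figure, without a causal reading of the before/after difference. This preserves comparison with the Background's 3.0 days.

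The cost is revised wording and a re-run on the same extracted data. The new measure overlaps in part with the primary outcome, which should be said. Statistical Methods is written in the past tense, the implementation phase was July 2022 and the document is dated March 2024. If results have already been seen, the analysis must be labelled post hoc and shown beside the planned one.

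### No planned analysis shows whether late prescriptions or return visits changed overall after feedback began; the one model that appears meant for them holds day-1 antimicrobial use fixed

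*Combined protocol and SAP*

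**What the plan says.** The Objectives section asks whether feedback "can safely reduce the unnecessary use of post-procedural antimicrobials in patients undergoing urologic procedures". The Safety outcomes section defines two binary outcomes: a late antimicrobial prescription at 7 to 30 days, and a return visit within 30 days.

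Under Interventions, the content delivered to sites is "Feedback on the percentage of patients who underwent a qualifying procedure and received an antimicrobial on post-procedural day 1". That is the primary outcome expressed as a percentage.

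Statistical Methods gives the primary outcome a logistic model in time, intervention phase and their interaction, fitted at each site separately. The secondary outcomes get the same model "with the addition of a fourth explanatory variable (a binary indicator for the primary outcome"). The reason given is: "This last variables was included to assess the risk of these secondary outcomes in patients who were not exposed", compared with those who were. On duration it says: "The median duration of post-procedural antimicrobial prescriptions at each site were compared using the Wilcoxon rank-sum test".

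Counts and percentages are planned for demographics, comorbidities and procedure types. Nothing is described that compares either safety outcome between phases without the day-1 indicator.

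**The concern.** Day-1 use lies on the path from feedback to safety. Feedback lowers day-1 use, and the safety question is what happens to patients as a result. A model that holds day-1 use fixed compares the phases among patients with the same exposure, so its intervention and interaction terms leave out any effect of treating fewer patients. They leave out the whole effect only if day-1 use is the sole pathway and use and outcome share no unmeasured cause. Otherwise they mix direct effects with confounding.

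The fourth coefficient answers a different question: how treated and untreated patients differ. It is a patient-level contrast adjusted only for time and phase, so confounding by indication can dilute or reverse it.

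The safety half of the objective therefore has no direct estimate. The Background says that the findings could inform a larger intervention across the VHA.

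**Working it through.** **1. Which outcomes the four-term model covers.** Only duration is listed under Secondary outcomes. Duration has its own rank-sum test, is not binary, and does not arise in unexposed patients. The model is logistic and speaks of the risk of plural outcomes in exposed and unexposed patients. I therefore read it as covering the two safety outcomes, which is an inference. Read literally, the safety outcomes have no model at all. On either reading, no estimate of their overall change is planned.

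**2. Inputs.** The documents give no safety event rates and no sample size to reproduce, so all rates below are assumed. From the documents: a 2-year baseline, July 2022 omitted, 1 year of intervention, separate models by site, time in days divided by 365, and a site minimum of 75 procedures a year. Assumed: day-1 use falls from 60% to 20% in one step, there is no secular trend, time is counted from the start of the intervention phase (the plan states no origin), and 200 procedures a year is the larger site volume. I fitted logistic models to the expected probabilities by day.

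**3. Overall risk by phase.** Overall risk = share exposed × risk if exposed + share unexposed × risk if unexposed.

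- Use protective (8% exposed, 14% unexposed): 0.6×0.08 + 0.4×0.14 = 0.104 at baseline; 0.2×0.08 + 0.8×0.14 = 0.128 under intervention. Odds ratio (0.128/0.872)/(0.104/0.896) = 1.26.
- Use harmful (14%, 8%): 0.116 to 0.092. Odds ratio (0.092/0.908)/(0.116/0.884) = 0.77.
- No effect (11% in both groups): 0.11 to 0.11. Odds ratio 1.00.

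| Assumed case | Three-term intervention OR | Four-term intervention OR | Exposure OR |
|---|---|---|---|
| Use protective | 1.26 | 1.00 | 0.53 |
| Use harmful | 0.77 | 1.00 | 1.87 |
| No effect, no confounding | 1.00 | 1.00 | 1.00 |

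The four-term intervention term misses the rise in the first case and the fall in the second.

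**4. Adding confounding by indication.** Suppose that patients with a clear indication stay treated in both phases, make up 5% to 16.1% of baseline exposed patients, and have a 20% to 40% event risk. The upper share borrows from the Background: 1 − 177/211 = 34/211 = 16.1%, in a prior cohort defined by more than 24 hours of use. The share in this trial is unknown.

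| Effect of use in other patients | Three-term intervention OR | Four-term intervention OR | Exposure OR |
|---|---|---|---|
| None | 1.00 | 1.03–1.28 | 1.07–1.82 |
| Protective | 1.21–1.26 | 1.03–1.28 | 0.60–1.15 |
| Harmful | 0.78–0.81 | 1.02–1.28 | 1.95–3.04 |

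In the first row overall risk does not change, yet both planned coefficients sit above 1. At the upper corner, overall risk is 0.0966×0.40 + 0.9034×0.11 = 0.138 in both phases, where 0.0966 = 0.6×0.161.

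**5. Precision per site, protective case.**

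| Estimate | 75/year, 95% CI | 200/year, 95% CI |
|---|---|---|
| Three-term intervention OR 1.26 | 0.22–7.3 | 0.43–3.7 |
| Four-term intervention OR 1.00 | 0.17–6.0 | 0.33–3.0 |
| Exposure OR 0.53 | 0.21–1.36 | 0.30–0.95 |
| Crude risk difference +2.4 points (Newcombe, ignores trend) | −5.9 to +12.6 | −2.8 to +8.4 |

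At 75/year the standard errors of the log odds ratios are 0.89 (three-term), 0.91 (four-term) and 0.48 (exposure). If time is instead counted from the start of baseline, the three-term interval at 75/year becomes about 0.003 to 617, because the intervention term is then extrapolated back to that date.

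**The case against.** The four-term model has a stated purpose, and risk with and without exposure is a fair stewardship question. It is not an invalid model. What is missing is a companion analysis. That stands, and the fix keeps the model.

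The primary outcome definition is also meant to limit confounding. The plan says: "This definition will be used to minimize the chance of including patients receiving antimicrobials for non-urologic or non-prophylactic indications". This may reduce the bias, but it cannot identify prophylaxis given to patients who were at higher risk to begin with. The upper corner in step 4 is severe: indicated patients would be 0.6×0.161/0.2 = 48% of remaining day-1 users. At 75/year the intervals there are 0.24 to 6.9 for the four-term intervention OR and 0.79 to 4.2 for the exposure OR, so a false signal would usually not reach significance at a small site.

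The three-term level change assumes a step, whereas feedback is repeated through the year. If use falls linearly from 60% to 20% over the year in the protective case, the three-term level OR is 1.00, like the four-term one. The change moves to the interaction: 1.26 per year, 95% CI 0.09 to 17.3 at 75/year and 0.26 to 6.3 at 200/year. This is correct. It means that the level and interaction terms must be read together and that the table of risks by phase matters at least as much as the model.

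Finally, this is a pilot with no sample size calculation, and the added estimate will rarely settle the question at one site. That is a reason to report intervals and absolute risks, not to leave the comparison out.

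**Conclusion.** The concern holds. Followed as written, the plan yields no number for the overall change in late prescriptions or return visits after feedback began, on either reading of the term secondary outcomes. That the existing model conditions on the targeted behaviour depends on reading that term as the safety outcomes, which the text supports but does not state.

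Size and direction in this trial are unknown. With assumed risks of 8% to 14% and use falling from 60% to 20% or 40%, the omitted overall odds ratio lies between 0.77 and 1.26 while the four-term intervention term stays at 1.00. This assumes that all of the effect runs through day-1 use and that there is no confounding. If use has no effect and there is no confounding, the models agree. The point should be fixed: safety is part of the objective and the remedy uses data already held.

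**What to change.** - Report the absolute risk of each safety outcome by phase and site, with the risk difference and its confidence interval.
- Fit the three-term model (time, intervention, interaction) to each safety outcome at each site, as the analysis of the programme's effect on safety.
- State the time origin and centre time at the start of the intervention phase. The intervention odds ratio is then the level change at that point and the interaction is the later change in slope. Interpret the two together.
- Keep the four-term model, labelled as an observational comparison of exposed and unexposed patients.
- State that secondary outcomes in Statistical Methods means the safety outcomes, if that is the intention.
- Label the added model post hoc if the planned analyses are done. Statistical Methods is in the past tense, so they may be.
- Do not read a non-significant result at a site as evidence of safety.

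The cost is SAP or report wording, six fits (2 outcomes × 3 sites) and one table, with no new data. The downside is imprecision. The added intervention term is no less precise than the planned four-term one but less precise than the exposure coefficient. It also remains an uncontrolled before/after comparison at sites chosen for high use.
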